The additional risk minimisation measures will include a Direct Healthcare Professional Communication (DHPC) that will be distributed to all healthcare professionals (HCPs) who are expected to be involved in the treatment and management of patients with diabetes; physicians, nurses, and where applicable, pharmacists who are expected to dispense medications for diabetes management. A patient communication document will be distributed to prescribing HCPs targeted for the DHPC. The DHPC will ask HCPs to provide the patient communication to patients receiving their initial prescription of Humalog 200 units/ml KwikPen. Where approved,

a web address link to the patient communication may be provided in the DHPC to allow either printing of the communication during the patient visit or provision of the link to the patient to enable the patient to directly access the communication.

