Humalog 200 units/ml KwikPen is a prefilled and multi-dose pen-injector device (pen) that delivers by subcutaneous injection insulin lispro for the maintenance of normal glucose homeostasis in adults with diabetes mellitus. Compared to Humalog 100 U/ml, it contains the same number of units of insulin lispro in half the volume. Despite warning messages on the pen and in the instructions for use, results from Human Factors studies performed in the US showed that a small percentage of patients may choose to withdraw insulin from the pen cartridge with a syringe if faced with device malfunction. Anecdotal information also indicates that patients in the EU may transfer insulin lispro from the pen cartridge into an insulin pump. Because of these data and to further optimise the benefit-risk balance of the formulation, additional Risk Minimisation Measures beyond routine risk minimisation measures (are being implemented, including communications to HCPs and patients to minimise the risk of hypoglycaemia and/or hyperglycaemia associated with insulin transfer from the pen cartridge to an alternative administration device without concentration adjustment and dose adjustment when transferring from Humalog 100 U/ml to Humalog 200 units/ml KwikPen.

**Non-Interventional Study Protocol
for Humalog 200 units/ml KwikPen
Version 1.0**

The additional risk minimisation measures include a DHPC that will be distributed to all physicians and nurses who are expected to be involved in the treatment and management of patients with diabetes and, where required, all pharmacists who are expected to dispense Humalog 200 units/ml KwikPen (HCPs). A patient communication document will be distributed to HCPs targeted for the DHPC. The DHPC will ask the HCPs to provide the patient communication to patients receiving their initial prescription of Humalog 200 units/ml KwikPen. Where approved, a web address link to the patient communication may also be provided in the DHPC to allow either printing of the communication during the patient visit or provision of the link to the patient to enable the patient to directly access the communication.

8. Research question and objectives

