- Extent of discussion between HCPs and patients when initially prescribing or dispensing Humalog 200 units/ml KwikPen (Did the HCP convey the key safety messages in the patient communication to patients when they received their initial prescription of Humalog 200 units/ml KwikPen?) with reference to the following safety messages.

Patients:

- Extent of understanding of the key safety messages for Humalog 200 units/ml KwikPen, as communicated through risk minimisation measures (Were the key safety messages in the patient communication understood by the patient?)
- Extent of recall/receipt of the patient communication or the means to access the patient communication from prescribers upon first prescription of Humalog 200 units/ml KwikPen (Does the patient recall receiving the patient communication document or the means to access from their HCP?)
- Extent of key safety message consideration by patients during administration of Humalog 200 units/ml KwikPen (Will the patient consider the safety messages communicated during administration of Humalog 200 units/ml KwikPen?)

9. Research methods

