9.1. Study design

This study is a multi-national, observational, cross-sectional survey design. Separate surveys will be administered to HCPs involved in the treatment and management of patients with diabetes and to patients with diabetes who have been prescribed Humalog 200 units/ml KwikPen. The study has been designed and will be executed and analysed in collaboration with UBC. The surveys have been developed to enable the study objectives to be met (Section 8).

User Testing was performed on each survey with a sample of 10 HCPs and 9 patients. The User Testing procedure was designed to assess comprehension among patients regarding the words and phrases used in select survey questions and response options. User Testing also assessed the clarity of the survey questions as presented to HCPs and the interest and acceptance of the surveys among all prospective respondents, flow and ease of completing the surveys, and preferred modes of administration. Findings and recommendations from User Testing have been incorporated into the surveys.

Assessment of the additional risk minimisation measures in the participating samples will be used to determine whether the target populations are aware of and adherent to the key message themes regarding the risk of hypoglycaemia and/or hyperglycaemia attributed to medication errors or misuse associated with the administration of Humalog 200 units/ml KwikPen. All statistical analyses will be descriptive, that is, no formal hypothesis will be tested. Study endpoints are as follows:

The tools will be considered effective if the majority of respondents demonstrate they are aware of the key risks communicated.

HCPs:

- Demonstrating that they understand the key safety messages communicated in the DHPC
- Reporting that they provided the patient communication or means to access the communication to patients at the time of first Humalog 200 units/ml KwikPen prescription
- Reporting they discussed the key safety messages in the patient communication with their patients who are receiving their first prescription of Humalog 200 units/ml KwikPen

Patients:

- Demonstrating that they understand the key safety messages communicated
- Reporting that they were provided with a copy of or means to access the Humalog 200 units/ml KwikPen patient communication from their HCP at the time of initial prescription
- Reporting that they consider the key messages during administration of Humalog 200 units/ml KwikPen

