- HCP medical specialty (for example, endocrinology, primary care)
- Number of years practicing medicine/nursing
- Number of Humalog 200 units/ml KwikPen-treated patients the HCP managed in the 12 month period preceding the survey (self-reported)

Data pertaining to evaluation of the effectiveness of the risk minimisation measures:

The survey includes questions/statements that will assess the risk understanding and behaviour of the HCPs. The understanding level and behaviours will be analysed using descriptive statistics and CIs and will be used to determine the effectiveness of the risk minimisation measures:

- Awareness of the DHPC on the correct use of Humalog 200 units/ml KwikPen
- Understanding of the key risk messages

- Self-reported practices with respect to communication of the key risk messages in clinical practice

Patients:

Screening questions:

- Agreement to participate
- Diagnosis of diabetes
- Prescribed Humalog 200 units/ml KwikPen
- 18 years or older
- Prior or current employment by Lilly, UBC, or any national medical governing body, such as but not limited to EMA, MHRA, and BfArM

Data on demographic characteristics:

- Age
- Sex
- Country
- Education status
- Length of time with diabetes
- Length of time on any insulin therapy
- Length of time on Humalog 200 units/ml KwikPen
- Length of time on Insulin used prior to Humalog 200 units/ml

Data pertaining to evaluation of the effectiveness of the risk minimisation measures:

The survey includes questions/statements that will assess the risk understanding and behaviour of patients. The understanding level and behaviours will be analysed using descriptive statistics and CIs and will be used to determine the effectiveness of the risk minimisation measures:

- Awareness of the Important Safety Information for Humalog 200 units/ml KwikPen
- Receipt of or access to the Important Safety Information
- Understanding of the key risk messages
- Patient behaviour with respect to the key risk messages

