 - The number of patients who responded to the invitation to participate in the survey
 - The number of patients eligible for participation in the survey
 - The number of ineligible patients along with the reasons for ineligibility
 - The number of eligible patients who completed the survey

- *Demographic characteristics of participants*
 - Distribution of participants by age groups
 - Distribution of participants by sex
 - Distribution of participants by country
 - Distribution of participants by years with diabetes
 - Distribution of participants by length of time treated with any injectable insulin therapy
 - Distribution of participants by length of time treated with Humalog 200 units/ml KwikPen
 - Distribution of participants by insulin used prior to Humalog 200 units/ml KwikPen
- *Patient responses to questions pertaining to the survey objectives:*
 - Awareness of the Important Safety Information for Humalog 200 units/ml KwikPen
 - Receipt of or access to Important Safety Information including the source of this information
 - Understanding of the risk messages
 - Self-reported practices with respect to the risk messages

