Thank you in advance for your participation. Please note the application will time out after 30 minutes of inactivity.

If you are ready to begin the survey at this time, please click continue. If not, click Return Later.

Please note: Do not use the browser's back button during this survey.

[END WELCOME PAGE]

16. Are you familiar with the patient communication: *IMPORTANT SAFETY INFORMATION FOR Humalog 200 units/ml KwikPen (insulin lispro)* provided by Eli Lilly and Company?

- Yes
- No **[GO TO Q18]**
- I don't know **[GO TO Q18]**

17. Did you read the patient communication: *IMPORTANT SAFETY INFORMATION FOR Humalog 200 units/ml KwikPen (insulin lispro)* provided by Eli Lilly and Company?

- Yes
- No
- I don't know

18. **[DISPLAY ONLY IN [ENTER COUNTRY THAT HAS WEBSITE]** Are you aware of the website [ENTER WEBSITE], at which patients can access the patient communication: *IMPORTANT SAFETY INFORMATION FOR Humalog 200 units/ml KwikPen (insulin lispro)*?

- Yes
- No
- I don't know

[DO NOT DISPLAY IF 0 IS SELECTED IN Q8]

[DISPLAY ONLY IN [ENTER COUNTRY THAT DOES NOT HAVE WEBSITE]
Do you or another healthcare professional at your practice provide the patient communication: *IMPORTANT SAFETY INFORMATION FOR Humalog 200 units/ml KwikPen (insulin lispro)*, to patients receiving their first prescription of Humalog 200 units/ml KwikPen?

19.

Do you or someone at your practice provide the patient communication: *IMPORTANT SAFETY INFORMATION FOR Humalog 200 units/ml KwikPen (insulin lispro)* or the website at which the communication can be accessed, to patients receiving their first prescription?

- Yes

- No
- I don't know

[DO NOT DISPLAY IF 0 IS SELECTED IN Q8]

20. Do you or another healthcare professional at your practice discuss the patient communication: *IMPORTANT SAFETY INFORMATION FOR Humalog 200 units/ml KwikPen (insulin lispro)* with patients at the time of initial prescription of Humalog 200 units/ml KwikPen?

- Yes
- No
- I don't know

[PHONE ONLY: BEGIN SAFETY EVENT]

(INTERVIEWER: Please record if respondent spontaneously reported a safety event or product complaint during the course of this interview.)

- Yes
- No **[GO TO END SAFETY EVENT SECTION]**

Enter Safety Event or Product Complaint Verbatim

[MULTILINE INPUT]

(INTERVIEWER: Refer to Project Specific Procedure for next steps.)

[END SAFETY EVENT]

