- Some secondary school (or EU equivalent) or less
 - Finished secondary school
 - Some university or completed technical/trade school
 - Graduated university
 - Post graduate studies
 - Prefer not to answer
11. In what country do you live?
- [DROP-DOWN LIST INPUT WITH COUNTRIES TABLE]**
12. Which of the following groups best describes your age?

- Under 18 **[TERMINATE AFTER Q12]**
 - 18 – 29
 - 30 – 39
 - 40 – 49
 - 50 – 59
 - 60 – 69
 - 70 or older
 - Prefer not to answer **[TERMINATE AFTER Q12]**
13. Have you or any of your immediate family members ever worked for Eli Lilly and Company (Lilly), United BioSource Corporation (UBC), or the European Medicines Agency (EMA)?
- Yes **[TERMINATE]**
 - No
 - I don't know **[TERMINATE]**

[END SCREENING QUESTIONS]

[BEGIN SURVEY CONTENT]

[PREAMBLE 2]

The following questions are about Humalog 200 units/ml KwikPen.

14. Please answer True, False, or I don't know for each of the following statements about Humalog 200 units/ml KwikPen.

	[RANDOMISE LIST]	True	False	I don't know
A	Humalog 200 units/ml should only be injected using the			

prefilled KwikPen device in which it is supplied.

- B Your dose of insulin does not need to be converted when changing from one strength of Humalog to the other (for example, changing from Humalog 100 U/ml to Humalog 200 units/ml KwikPen).

15. Please answer Yes, No, or I don't know for each of the following statements about the patient communication titled *IMPORTANT SAFETY INFORMATION FOR Humalog 200 units/ml KwikPen (insulin lispro)*.

- | | Yes | No | I don't know |
|---|-----------------------|-----------------------|-----------------------|
| 
[RANDOMISE LIST]
 
[DISPLAY ONLY IN [ENTER COUNTRIES THAT DO NOT HAVE WEBSITE]]The first time I was prescribed Humalog 200 units/ml KwikPen, my doctor or nurse provided me with a paper copy of IMPORTANT SAFETY INFORMATION FOR Humalog 200 units/ml KwikPen (insulin lispro).
 |  |  |  |
| 
A [DISPLAY ONLY IN [ENTER COUNTRIES THAT HAVE WEBSITE]]The first time I was prescribed Humalog 200 units/ml KwikPen, my doctor or nurse provided me with a paper copy or told me to access the website to view IMPORTANT SAFETY INFORMATION FOR Humalog 200 units/ml KwikPen (insulin lispro).
 |  |  |  |

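### Patient awareness of the Important Safety Information is a listed effectiveness measure, but no patient survey item asks about it, and the protocol disagrees on who supplies the leaflet that the receipt item asks about

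*Protocol*

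**What the plan says.** **Measures.** Protocol Section 9.4 (Patients) lists four kinds of data that will be used to determine effectiveness. The first is "Awareness of the Important Safety Information for Humalog 200 units/ml KwikPen"; receipt of or access to the document is a separate entry. Section 9.7 repeats both as reported results and widens the second to "Receipt of or access to Important Safety Information including the source of this information".

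**Endpoint.** Section 9.1 ties the patient receipt endpoint to the first prescription and defines it as "Reporting that they were provided with a copy of or means to access the Humalog 200 units/ml KwikPen patient communication from their HCP".

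**Who supplies the leaflet.** The abstract, Section 4.1, says "A patient communication document will be distributed to prescribing HCPs targeted for the DHPC". Section 7 drops the limit to prescribers: "A patient communication document will be distributed to HCPs targeted for the DHPC". It counts dispensing pharmacists in that group where required. The patient research question in Section 8 speaks of receipt from prescribers.

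**Survey.** In website countries Q15A asks whether, at first prescription, "my doctor or nurse provided me with a paper copy or told me to access the website to view" the document. Elsewhere it asks about a paper copy only, again from a doctor or nurse.

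**The concern.** A measure that the protocol says will inform the effectiveness judgement needs a question behind it. An analysis plan cannot supply one afterwards. Section 9.6 rules out queries to respondents, and Section 9.4 says access codes are neither tracked nor reusable, so the gap cannot be closed once data collection starts.

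The second issue is that the receipt item is narrower than the receipt endpoint if HCP has its Section 7 meaning. Section 9.9 says that a respondent who reports not receiving the communication counts towards a finding of less than optimal dissemination. If pharmacists hand out the leaflet in a study country, a truthful No to Q15A would be read that way although the patient had the leaflet.

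**Working it through.** **1. Match each listed patient measure to the survey.** Appendix I.3 is numbered continuously from Q1 to Q16. Q1 to Q13 are screening and demographic items. The rest are:

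| Item | What it asks | Measure served |
|---|---|---|
| Q14A, Q14B | Two key messages, true or false | Understanding |
| Q15A | Doctor or nurse gave the document (or, in website countries, pointed to the website) at first prescription | Receipt or access |
| Q15B | Doctor or nurse offered to explain it | Discussion |
| Q15C | Patient thinks about the safety information when injecting | Behaviour |
| Q16 | Sources of safe-use information other than doctor or nurse | Source, but not of this document |

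No row serves awareness. A Yes to Q15C suggests some awareness. A No does not show its absence, because a patient may know of the document and not think about it when injecting.

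**2. Compare with the HCP survey.** Appendix I.1 Q16 asks HCPs whether they are familiar with the same patient communication, and Q17 asks "Did you read the patient communication". The patient survey has no counterpart to either.

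**3. Set the supplier wording side by side.**

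| Place | Supplier |
|---|---|
| Section 4.1 | Prescribing HCPs |
| Section 7 | All HCPs targeted for the DHPC, with pharmacists where required |
| Section 8, patient question | Prescribers |
| Section 9.1, patient endpoint | The patient's HCP |
| Appendix I.3, Q15A and Q15B | Doctor or nurse |

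Q15A fits Sections 4.1 and 8. It is narrower than Section 9.1 read with Section 7.

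**4. Can Q16 fill the gap?** It offers Pharmacist and Internet as options, so contact with a pharmacist is visible. It asks about information on safe use in general, though. A pharmacist's spoken advice and a pharmacist's copy of the leaflet produce the same answer, so neither receipt of the leaflet nor its source can be recovered.

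**5. Can the effect on receipt be sized?** Let R be true receipt from any HCP and f the share of recipients who got the leaflet only from a pharmacist. Then the Q15A proportion is R × (1 − f). The document gives neither value, so the figures below are assumptions:

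- R = 60%: f = 10% gives 60 × 0.90 = 54%; f = 20% gives 60 × 0.80 = 48%.
- R = 80%: f = 10% gives 80 × 0.90 = 72%; f = 20% gives 80 × 0.80 = 64%.
- f = 0 (no pharmacist route): no shift.

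For scale, the half-width in Section 9.5, Table 1 reproduces: 1.96 × √(0.6 × 0.4 / 280) = 5.7 points at 60%, and 1.96 × √(0.8 × 0.2 / 280) = 4.7 points at 80%. The 10% shifts of 6 and 8 points would exceed these, but whether any shift occurs is unknown.

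**The case against.** The strongest reply is that the receipt item does what the protocol asks, and much of that stands.

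- **Unopened material.** A reader might infer that Q15A overstates reach because a patient told of the website who never opened it answers Yes. The documents do not support calling this an error. The endpoint is a copy or a means to access, and such a patient was given the means.
- **Pharmacists.** A reader might infer that pharmacist-supplied patients will be scored as not reached. No scoring rule says so: the correct or incorrect coding in Section 9.7 applies to the key risk messages. Pharmacists enter only where applicable (Section 4.1) or where required (Section 7), no study country is said to use them, and the third country is still open. The Section 8 wording "Extent of discussion between HCPs and patients when initially prescribing or dispensing Humalog 200 units/ml KwikPen" is in the HCP list and concerns discussion, so it is weak evidence about patient receipt.
- **The majority line.** A reader might infer that receipt could be pushed below a majority. That depends wholly on the assumed shares: at 80% true receipt it stays well above.
- **Consequence.** Awareness of the document is not among the Section 9.1 endpoints, and no comparison of readers with non-readers is planned.

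None of this answers the main point. Sections 9.4 and 9.7 still list awareness as its own result, and the survey has no item for it. The supplier wording still conflicts, and Q16 still does not name the document whose source Section 9.7 promises to report.

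**Conclusion.** The point holds in a limited form. The missing awareness item is certain: it follows from reading the listed measures against the survey and rests on no assumption. The conflict over who supplies the leaflet is also plain on the page. Loss of pharmacist receipt is conditional on that route being used in a study country, and its size cannot be derived from the protocol. The understanding items in Q14, which serve the primary objective, are not affected. This should be corrected before the survey is translated and fielded, but it does not undermine the main result.

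**What to change.** 1. Between Q14 and Q15, add two closed patient items (Yes, No, I don't know) modelled on HCP Q16 and Q17: familiar with the Important Safety Information document, and read it. Respondents cannot go back, so this position keeps the new items from prompting the Q14 answers.
2. Report awareness from the first item, and reading as a separate descriptive result. Keep Q15A (copy or means to access) as the receipt endpoint; do not redefine access as having read. If the items are not wanted, delete awareness from Sections 9.4 and 9.7.
3. Reconcile Sections 4.1, 7, 8 and 9.1 on who supplies the leaflet. If pharmacists are included, add them to Q15A and Q15B.
4. Reword Q16 so that it asks about the source of the Important Safety Information document.

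The cost is two more closed questions, small wording changes and their translation. Annex 1 still lists the patient survey as a draft, so the change is cheap now and cannot be made good after data collection.

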9.4.1. Data collection process

The survey start date will be within 18 months from product launch in the individual countries. This date will vary by country based on market uptake. Survey data collection will be closed when the desired number of surveys have been completed.

The Internet survey will be self-administered. For the telephone survey, a trained interviewer from the Survey Coordinating Centre will conduct the telephone interviews using a Computer-Assisted Telephone Interviewing (CATI) programme and enter participant responses directly into the EDC while in conversation with the respondent. Questions are programmed to ensure that they are asked in the appropriate sequence and skip patterns are clearly indicated.

Respondents cannot go back to a question once the question has been answered and they cannot

skip ahead. Statements requiring response and response options presented in a list are randomised to minimise positional bias. Paper surveys, if employed, will have instructions to guide respondents through the survey correctly and a Call Centre Associate (CCA) will enter the responses into the EDC verbatim from the paper survey received.

Follow-up reminder process

HCPs:

The database of invited HCPs will be routinely updated with responders and after each mailing, the database will be cross-checked with any correspondence that had an invalid address, bounced back or had incorrect contact details. The target sample for survey reminders is HCPs who received the invitation (that is, no reason for not receiving, such as invalid address) but did not respond within 2 weeks from initial mailing. Using the updated database, at least one reminder will be sent to the sample defined above. The total number of reminders will be based on the response rate at predefined recruitment milestones identified by Lilly. The interval between the reminders will be approximately 2 to 3 weeks.

Patients:

The response rate will be closely monitored and reminders will be sent to HCPs periodically. After each mailing, the database will be cross-checked with any correspondence that had an invalid HCP address, were returned as undeliverable or had incorrect contact details. The target sample for survey reminders is HCPs who received the request to invite eligible patients to participate in the survey (that is, no reason for not receiving, such as invalid address) in the initial mailing. Using the updated database, at least one reminder will be sent to the sample defined above. The total number of reminders will be based on the response rate at predefined recruitment milestones identified by Lilly. The interval between the reminders will be approximately 2 to 3 weeks.

